### 2 Statistical analysis plan

Statistical analyses will be calculated using SAS 9.2 statistical analysis software.

The primary validity analysis dataset will be FAS, and PPS will also be analyzed.

All statistical tests will be two-sided, and a p-value of less than or equal to 0.05 will be considered a statistically

The differences tested were considered statistically significant.

Measures for each visit in the different treatment groups were described statistically as mean  $\pm$  standard deviation. Comparisons were made with the baseline values at the time of enrollment using the paired t-test. The paired t-test was used to compare pre- and post-treatment differences within groups. Changes before and after treatment in each group were compared using analysis of variance (ANOVA). The count data of each visit of different treatment groups were statistically described by frequency counts (constitutive ratio). Changes before and after treatment in each group were analyzed using the  $\chi^2$  test or nonparametric The  $\chi^2$  test or non-parametric test was used.

Shedding analysis: The  $\chi^2$  test will be used to compare the total shedding rate and the shedding due to adverse events in each group.

Balanced analysis of baseline values: ANOVA or  $\chi^2$  test will be used to compare demographic data and other baseline indicators to measure how well balanced the two groups are. measure how well the two groups are balanced.

Effectiveness analysis: PPS and FAS were used to analyze the primary and secondary indicators; since this study is a multicenter clinical trial, the impact of central effects on the efficacy indicators should be considered in the analysis. Since this study is a multicenter clinical trial, the influence of center effect on the efficacy indexes should be considered in the analysis.

Safety analysis: the X test was used to compare the incidence of adverse events in the two groups, and the adverse events occurred in this trial were described in a list. Adverse events: the X test was used to compare the incidence of adverse events in the two groups, and the adverse events occurred in this trial were described in a list; the changes of normal/abnormal laboratory test results before and after the trial were analyzed, as well as the relationship between the abnormal changes and the test drug. Safety analysis: The X test was used to compare the incidence of adverse events in the two groups and to describe the adverse events in this trial.

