6.2 Diagnostic indicators

Tumor pathology, staging, symptom-based anorexia assessment, TCM evidence.

6.3 Main observational indexes: refer to the "Anorexia Diagnosis and Treatment Pathway" of the Professional Committee of Tumor Nutrition and Supportive Therapy of the Chinese Anti-Cancer Association.

① Symptom-based anorexia evaluation form: Appendix I.

② Simplified Appetite Scale: Appendix V.

6.4 Secondary observation indicators:

① Fatigue Symptoms Scale: Appendix III.

② Patient's expectation of acupuncture: Appendix II. Appendix II

Appetite level: VAS is a semi-quantitative assessment of the degree of anorexia nervosa.

Drawing on the practice of foreign countries in the last century and the idea of VAS assessment for cancer pain in China, it is suggested that a 10 cm long travel scale with 10 scales on one side and "0" and "10" marks on the other side should be used. The scale has 10 marks on one side, with the "0" and "10" markings on both ends, with the "0" marking indicating a normal appetite and the "10" marking indicating an extreme aversion to food. When using the graduated side of the back to the patient, let the patient in the ruler marked on the degree of their desire for food on the corresponding position, the physician according to the position marked by the patient for its score, clinical evaluation to "0-2" is "normal appetite / basic normal eaters The clinical assessment is "0-2" as "normal appetite/basic normal eater", "3-5" as "mild anorexia", "6-8" as "moderate anorexia", and >8 as "anorexia". The score of "3-5" was classified as "mild anorexia", "6-8" as "moderate anorexia", and ">8" as "severe anorexia". The efficacy of the treatment was evaluated according to the change in appetite. Effective: improvement level greater than or equal to 1; stable: no change in level; ineffective: decrease in level.

④ Weight. Weight changes caused by factors other than fluid accumulation in the body cavity and swelling. Improvement: weight gain >2Kg and maintained for more than 4 weeks. Stable: weight gain or loss of ≤ 2 Kg. deterioration: weight loss of >2Kg. 5.

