## Statistical analysis

### 1 Statistical analysis data set

#### ① Full Analysis Set (FAS)

is the ideal set of subjects that is as close as possible to the principle of intentional analysis (the primary analysis is to include all randomized subjects), and which is derived from the smallest and reasonably methodologically sound elimination of all randomized subjects. Estimates of missing values for the primary variables were carried forward (carry-forward) to the point where trial data were missing using the Last Observation Carry Forward (LOCF) method, with the number of subjects evaluating efficacy at endpoint remaining the same for each group as at the start of the trial. the FAS population was used for the analysis of the primary and secondary efficacy measures.

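### The planned between-arm ANOVA of change is valid but leaves out the baseline score, and the SAP does not say that efficacy rests on it rather than on the within-arm paired tests

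*SAP*

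**What the plan says.** SAP section 2 applies one threshold to every test: "All statistical tests will be two-sided, and a p-value of less than or equal to 0.05 will be considered a statistically" significant difference (the sentence breaks off in the available text). For measured scores it then lists, in sequence:

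- a comparison of each visit with enrolment: "Comparisons were made with the baseline values at the time of enrollment using the paired t-test";
- the same test, labelled as within-arm: "The paired t-test was used to compare pre- and post-treatment differences within groups";
- a test of change: "Changes before and after treatment in each group were compared using analysis of variance (ANOVA".

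The only other use of baseline values is a balance check by ANOVA or chi-square. No covariate is named. The effectiveness paragraph gives the analysis sets (FAS and PPS) and mentions a centre effect, but names no test or contrast that decides efficacy. Count data go to chi-square or nonparametric tests. Under SAP section 1 (FAS), missing values of the primary variables are filled "using the Last Observation Carry Forward (LOCF) method".

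Protocol section 6.3 has two main outcomes, "Symptom-based anorexia evaluation form: Appendix I" and "Simplified Appetite Scale: Appendix V", and section 6.5 schedules both at weeks 2, 4 and 8. Under section 5.2 both arms receive conventional nutritional support and symptomatic treatment, and either may have chemotherapy or radiotherapy. Section 2 calls the study exploratory, with 30 per arm and no power target, effect size or SD.

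One block of the SAP was removed before review. Statements here about what is absent cover the remaining SAP text and the Protocol.

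**The concern.** Two things are left open.

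The first is precision. A change score subtracts the whole baseline value, whatever the correlation between baseline and follow-up. ANCOVA estimates how much of the baseline to subtract, and so gives a less variable treatment contrast from the same data. With 60 patients that is worth having.

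The second is interpretation. A paired test within the needling arm cannot separate needling from the conventional care that both arms get, from anticancer treatment, or from the course of the disease. The SAP lists these tests beside the between-arm test at the same level and does not say which supports an efficacy claim. If both arms improve alike, a significant result in one arm and not in the other could be reported as benefit although the randomised comparison shows none.

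**Working it through.** The plan gives no figure to reproduce, because the sample size has no stated inputs. From the documents: 30 per arm, two-sided 0.05. Assumed, since the documents give neither: baseline to follow-up correlation r = 0.3–0.7, and the sizes of common change below.

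**1. Which contrast is the ANOVA?** The paired test is expressly the within-arm one. The phrase about each group also occurs where the SAP plainly compares the arms on dropout, by a chi-square test to "compare the total shedding rate and the shedding due to adverse events in each group". The ANOVA of change is therefore most naturally the between-arm test.

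**2. Precision, score not restricted at entry** (variances in units of the population variance).
- Change score: 2(1 − r). ANCOVA: 1 − r². Ratio: (1 + r)/2 = 0.65 at r = 0.3 and 0.85 at r = 0.7.
- Cost of estimating the slope: 1 + 1/(60 − 4) = 1 + 1/56. Net ratio 0.662 to 0.865, a saving of 13–34%.
- Difference detectable with 80% power, 30 per arm, noncentral t: 0.736 SD of the analysed variable. For change, multiply by √[2(1 − r)]: 0.87 (r = 0.3) and 0.57 (r = 0.7). For ANCOVA, multiply by √[(1 − r²)(1 + 1/56)]: 0.71 and 0.53.

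**3. Precision on the symptom scale if entry requires ≤ 24.** Protocol section 3.1.1 sets this as the diagnostic criterion. The inclusion list in section 4.1 is garbled in the available text (item 1 three times, no item 2), so the cut-off as an entry rule is probable but unconfirmed. Assume a source mean μ of 20–28 and SD 7.
- a = (24 − μ)/7; λ = φ(a)/Φ(a); remaining baseline variance v = 1 − aλ − λ². This gives v = 0.506 at μ = 20 and 0.257 at μ = 28.
- Change-score variance: (1 − r)²v + 1 − r². ANCOVA variance: 1 − r², times 57/56 for the slope.

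| r | μ | change variance | net ratio | detectable, change | detectable, ANCOVA |
|---|---|---|---|---|---|
| 0.3 | 20 | 0.49 × 0.506 + 0.91 = 1.158 | 0.800 | 0.79 | 0.71 |
| 0.3 | 28 | 0.49 × 0.257 + 0.91 = 1.036 | 0.894 | 0.75 | 0.71 |
| 0.7 | 20 | 0.09 × 0.506 + 0.51 = 0.556 | 0.935 | 0.55 | 0.53 |
| 0.7 | 28 | 0.09 × 0.257 + 0.51 = 0.533 | 0.974 | 0.54 | 0.53 |

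The net saving is about 3–20%.

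**4. The within-arm pattern.** Suppose both arms truly improve by the same d (in SDs of change), so that needling adds nothing. With n = 30, critical t 2.045 and noncentrality d√30, let p be the chance that one arm shows significant improvement. Needling significant and control not then has probability p(1 − p).

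| d | p | p(1 − p) |
|---|---|---|
| 0.1 | 0.076 | 0.071 |
| 0.2 | 0.184 | 0.150 |
| 0.3 | 0.355 | 0.229 |
| 0.4 | 0.563 | 0.246 |
| 0.5 | 0.754 | 0.186 |
| 0.6 | 0.888 | 0.099 |
| 0.7 | 0.959 | 0.039 |

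The maximum, 0.250, is at d = 0.37. In simulation (40,000 trials per cell) the between-arm test was not significant in 86–90% of the trials showing this pattern at d = 0.2–0.5. Carrying baseline forward in 10–20% of patients leaves the range at 13–25%. If both arms instead worsen by 0.2–0.5 SD, the pattern is about 0.1% or less, but its mirror image (control significantly worse, needling not) has the same 15–25%.

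**5. Validity of the planned test.** When both arms improve equally, the simulated type I error of the between-arm test of change was 4.8% and 5.2% (d = 0.365 and 0.5), in line with the nominal 5%.

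**The case against.** The strongest reply is that nothing here is an error. A valid between-arm test is planned, the paired tests are labelled as within-arm, the design is randomised and parallel, and an exploratory trial without a power target misses no stated goal by giving up some precision. All of that stands.

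Three stronger readings are tempting, and the documents support none of them:

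- **That no between-arm test is planned.** The wording is loose, but its context points to a comparison of the arms.
- **That the trial has a 15–25% false-positive rate.** That figure is the frequency of a pattern which the SAP nowhere adopts as a decision rule. It also depends on the assumed common improvement, and is 7% at 0.1 SD, 10% at 0.6 SD and 4% at 0.7 SD.
- **That an ANOVA of change is biased or inflates type I error.** Under randomisation it does neither.

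It is also fair to say that the larger precision figures may not apply to the first main outcome. If entry is cut at 24, the saving there is the smaller 3–20%. SNAQ, if correlated with the symptom score, may also save less than the unrestricted figure.

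The reply does not remove two facts: the SAP neither names the deciding contrast nor excludes the within-arm results from efficacy conclusions, and a more precise analysis is available from data that the paired tests already require.

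**Conclusion.** The point holds as an improvement in precision and clarity at almost no cost. It does not invalidate the planned test.

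- **Precision.** For assumed r = 0.3–0.7, the net variance saving is about 13–34% on scores not restricted at entry. On the symptom scale with entry at ≤ 24 (source mean 20–28 and SD 7 assumed) it is about 3–20%; the detectable difference there falls from about 0.75–0.79 to 0.71 SD at r = 0.3, and from about 0.54–0.55 to 0.53 SD at r = 0.7.
- **Interpretation.** The within-arm tests create a risk of misreading, with the misleading pattern in 15–25% of trials if both arms improve equally by an assumed 0.2–0.5 SD of change. Whether anyone would draw that inference is not something the documents settle.

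SAP section 2 also calls the trial multicentre, whereas Protocol section 3 recruits from one department of one hospital. That is a separate matter to reconcile and adds no weight here.

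**What to change.** In SAP section 2:

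1. For the continuous scores measured at baseline and follow-up, replace the ANOVA of change with ANCOVA of the follow-up score on arm plus that outcome's own baseline. These are the symptom-based anorexia score, SNAQ, the FSI scores, the appetite VAS, weight and KPS. Report the adjusted between-arm difference with its 95% CI.
2. State that efficacy conclusions rest on this contrast, either for one main outcome and visit named in advance, or for both main outcomes with a stated multiplicity adjustment.
3. Show within-arm changes descriptively, without p-values.
4. Keep chi-square or nonparametric between-arm tests for the graded responses in Protocol section 6.4 (appetite level, weight, Karnofsky). Do not apply the ANCOVA to the acupuncture expectation questionnaire, which has no scheduled follow-up in section 6.5.

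**Cost:** SAP wording and one degree of freedom, already counted in the net savings above. No added patients or visits. Confirm that the CRF records each scale at baseline: Protocol section 6.5.1 refers only to the CRF, although the planned comparison with enrolment values implies it.

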
This research proposal is in response to the National Natural Science Foundation of China's top-level project (Project No. 81573958; Title:

Auricular Acupuncture for Clinically Advanced Tumor Patients' Appetite Intervention and Mechanism Research).

Research Objectives

To objectively evaluate the clinical efficacy of auricular acupuncture in improving the appetite of tumor patients, to verify and improve its technique, to determine the therapeutic points and treatment course, and to provide a strong evidence-based medical basis for auricular acupuncture intervention in tumor therapy. We will validate and improve its technique, determine the therapeutic points and treatment course, and provide a strong evidence-based

medical basis for the intervention of auricular acupuncture in the treatment of tumors.

Research content

1 Type of study design

This study used a randomized, parallel-controlled research method. Based on the principle of voluntary participation, baseline information was included and collected, random seeds were generated by the SAS 9.2 statistical software random seed generator, and in a ratio of 1:1, it was proposed to randomly assign 60 subjects meeting the inclusion criteria to the ear acupuncture group and the control group. Each group of 30 cases, statistical expert design, after the preparation of the randomization scheme, the control and implementation of the allocation by those who are not directly involved in the grouping.

2 Sample size setting

This study was an exploratory study, considering 30 cases in each group, totaling 60 patients.

3 Study population

Sixty patients with anorexia nervosa of malignant tumors of stage III and IV who attended outpatient clinics or were hospitalized in the Department of Oncology of Xiyuan Hospital of China Academy of Traditional Chinese Medicine from May 1, 2016 to October 31, 2017.

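### Baseline p-values at 30 per arm cannot measure balance, and the between-arm ANOVA of change names no baseline covariate; prespecified ANCOVA would remove conditional bias and gain precision at almost no cost

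*SAP*

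**What the plan says.** The SAP, section 2 (Statistical analysis plan), gives the baseline tests a purpose: "ANOVA or $\chi^2$ test will be used to compare demographic data and other baseline indicators to measure how well balanced the two groups are". The only threshold in that section is general: "All statistical tests will be two-sided, and a p-value of less than or equal to 0.05 will be considered" significant. It gives no size of difference that would count as an imbalance, and no consequence for a significant or a non-significant baseline result.

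The same section tests within-group change by paired t-test and compares changes before and after treatment by ANOVA. I read the ANOVA as the between-arm comparison. No baseline score or prognostic factor is named as a covariate. Centre is the only factor to be taken into account.

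The protocol's section 2 (Sample size setting) states: "This study was an exploratory study, considering 30 cases in each group, totaling 60 patients". Its section 1 allocates patients "in a ratio of 1:1, it was proposed to randomly assign 60 subjects", and no stratification is described.

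**The concern.** A significance test of baseline data in a randomised trial asks whether the difference arose by chance. If the randomisation was sound, the answer is known to be yes. The p-value does not say how large the difference is or whether it matters for the outcome, yet the SAP uses the test as a measure of balance.

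This matters more in a small, mixed population. The protocol admits stage III and IV malignancy without naming a tumour type, KPS from 60 upwards, ages 18 to 80, and patients with or without chemotherapy or radiotherapy. If a prognostic factor differs between arms, the reader has a p-value that is unlikely to flag it and an efficacy comparison that does not adjust for it. The arm difference in appetite score could then partly reflect who was allocated where. Variation that baseline data could explain also stays in the error term.

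**Working it through.** **Inputs.** 30 per arm and 1:1 allocation (protocol sections 1 and 2). Two-sided 0.05 (SAP section 2). The full analysis set keeps its starting numbers through last observation carried forward (SAP section 1), so 30 per arm applies at the endpoint. The documents give no SD, no baseline-outcome correlation (ρ) and no balance threshold, so there is no figure of the plan's own to reproduce. ρ is an assumption throughout, shown as a range. Equal SDs at baseline and follow-up are also assumed.

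**1. What the baseline test can flag.** For two arms, ANOVA is the t-test. In SD units the standard error of a difference in means is √(2/30) = 0.258, with 58 degrees of freedom.

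- Smallest significant observed difference: t(0.975, 58) × 0.258 = 2.002 × 0.258 = 0.517 SD.
- Observed difference of 0.5 SD: t = 0.5/0.258 = 1.94, p = 0.058.
- Binary example, 18/30 v 11/30 (60% v 37%): χ² = 60 × (18×19 − 11×12)² / (30×30×29×31) = 2,646,000/809,100 = 3.27, p = 0.07.

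Neither example is flagged. By the same p-value, a difference of 0.5 SD or more on one given continuous variable arises by chance in about 5.8% of randomisations.

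**2. Imbalance in the outcome's own baseline.** Take an observed imbalance d = 0.5 SD and no treatment effect. The expected follow-up difference is ρd, so the expected difference in change is (ρ − 1)d. The SD of change is √(2(1 − ρ)), so its standard error is 0.258 × √(2(1 − ρ)).

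| ρ | Difference in change (SD) | SE | Shift in SE |
|---|---|---|---|
| 0.2 | −0.40 | 0.327 | −1.22 |
| 0.5 | −0.25 | 0.258 | −0.97 |
| 0.8 | −0.10 | 0.163 | −0.61 |

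Subtracting the baseline over-corrects: the shift runs against the baseline difference.

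**3. Imbalance in another prognostic factor.** If the factor has correlation ρ with the analysed outcome, the unadjusted comparison shifts by 0.5ρ/0.258. That is 0.58, 0.97 and 1.36 SE for ρ = 0.3, 0.5 and 0.7. Simulation with the observed imbalance held at 0.5 SD and no treatment effect gave false-positive rates of about 8%, 12% and 19%. With the factor as a covariate the rate was about 5% in each case.

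**4. Averaged over randomisations.** In 200,000 simulated null trials per correlation (0.3, 0.5, 0.7), the unadjusted test rejected in 4.9% to 5.1%. Among trials whose baseline test was non-significant it rejected in 4.8%, 4.3% and 3.5%.

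**5. Precision.** Residual variance is 1 − ρ² for ANCOVA on the baseline score and 2(1 − ρ) for change scores. The ratio is (1 + ρ)/2, which is 0.60, 0.75 and 0.90 for ρ = 0.2, 0.5 and 0.8. At ρ = 0.5 the baseline covariate alone cuts variance by 25%.

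**The case against.** The strongest defence is that randomisation already protects the unadjusted comparison. Type I error is about 5% overall and slightly lower among trials that pass the baseline test, as step 4 shows. An imbalance as large as 0.5 SD on any one variable is uncommon, and it lies close to the largest that can go unflagged. All of this stands. Mixed tumour types and performance status widen the SD; they do not make a standardised imbalance more likely. The conditional rates in step 3 describe one unlucky allocation and must not be read as the trial's error rate.

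Second, the SAP does not say that a non-significant test means the groups are balanced, or that any later analysis depends on the result. A reader might infer such a rule from the stated purpose of the tests, but it is not written down. The SAP also plans means, SDs and frequencies by arm, so the size of a difference can be read from the tables.

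Third, change scores already use each patient's baseline. True, but step 2 shows that they do not remove an imbalance in it, and they do nothing for KPS or stage unless change is unrelated to those factors.

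Fourth, the trial is labelled exploratory. That lowers the stakes but is no reason to leave precision unused with 60 patients.

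**Conclusion.** The point holds as one about precision and conditional bias. The planned tests do not measure balance at 30 per arm, and no baseline adjustment for prognostic imbalance is named.

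Three stronger readings are tempting and are not supported:

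- **That the tests miss a 0.5-SD imbalance about half the time.** The 52% figure is one minus the power against a true population difference, which randomisation makes zero. An observed 0.5-SD difference is never significant at this sample size.
- **That the trial's false-positive rate is inflated.** It is not, when averaged over randomisations.
- **That the efficacy result will be off by about one standard error.** That needs both a 0.5-SD imbalance and a correlation near 0.5, and the documents give neither.

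The sizes in steps 2, 3 and 5 rest on the assumed correlations and on equal SDs at baseline and follow-up. Requiring an anorexia score of 24 or below at entry may narrow the baseline spread of that scale, so the true values could differ. Removing the baseline p-values would by itself change no efficacy result; the gain comes from the covariates.

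**What to change.** In SAP section 2, make two changes.

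1. **Efficacy model.** State that each continuous efficacy outcome will be compared between arms by ANCOVA, with the baseline value of that outcome, baseline KPS and stage (III v IV) as covariates. Fix these before the data are analysed and use them whatever imbalance is observed. When KPS is itself the outcome, its baseline value already serves as the KPS covariate.
2. **Baseline description.** Replace the balance tests with summaries by arm (mean and SD, or number and percentage) and standardised differences. State that balance will not be inferred from p-values.

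No new data are needed. KPS is an inclusion criterion (protocol 4.1), stage is a diagnostic indicator (6.2), and the SAP already compares each visit with enrolment values. Residual degrees of freedom fall by about three, from 58 to 55 before any centre term, which moves the critical t from 2.002 to 2.004. The rest is SAP wording and a few lines of SAS code.

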5.2 Treatment program

5.2.1 Ear acupuncture group

Ear acupuncture treatment + conventional nutritional support and symptomatic treatment (refer to "Diagnostic and therapeutic path of anorexia nervosa" of tumor nutrition and supportive therapy committee of China Anti-Cancer Association).

Commonly used main points: Shenmen, stomach, spleen, subcortex.

Auxiliary points: Sanjiao, sympathetic, liver, small intestine.

Methods: Embed an earring needle and fix it with adhesive tape, press each point for about 2 minutes each time, 2-3 times a day, the pressure depends on the tolerance of the individual, alternating between the two ears, 2-3 times a week, 4 weeks of treatment, observation until 8 weeks.

5.2.2 Control group: Conventional nutritional support and symptomatic treatment.

During the treatment period, both groups can use supportive therapy reciprocally, if there are treatment-related adverse events, they should be handled separately, and the causes, history, symptoms and treatment measures should be recorded in detail. During the treatment period, both groups of cases could adopt the international standard protocol (Version 3.2014 NCCN) with or without standard chemotherapy or or without standard chemotherapy or radiation therapy.

6 Observation Indicators

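### The SAP calls the trial multicentre and asks for the centre effect to be considered, but the protocol recruits from one hospital department, so the instruction is empty and scores are left to an ANOVA of changes with no covariate

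*SAP*

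**What the plan says.** **Number of centres.** SAP section 2, under the effectiveness analysis, states that "since this study is a multicenter clinical trial, the impact of central effects on the efficacy indicators should be considered in the analysis". It does not say how: no model, term or pooling rule for centre is given. Protocol section 3 describes the study population as sixty patients "who attended outpatient clinics or were hospitalized in the Department of Oncology of Xiyuan Hospital", between two stated dates. The randomisation text in protocol section 1 ("in a ratio of 1:1, it was proposed to randomly assign 60 subjects") and section 5.1 mentions neither centre nor any stratification factor.

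**Between-group analysis.** SAP section 2 assigns paired t-tests to the within-group comparisons with baseline. For scores it then says "Changes before and after treatment in each group were compared using analysis of variance (ANOVA"), and for counts it gives a chi-square or non-parametric test. I read the ANOVA as the between-group comparison. No covariate is named. Baseline balance is to be tested, but nothing is said about what follows if the groups differ.

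**Size and concurrent treatment.** Protocol section 2: "This study was an exploratory study, considering 30 cases in each group, totaling 60 patients". Protocol section 5.2 says that "both groups of cases could adopt the international standard protocol (Version 3.2014 NCCN) with or without standard chemotherapy", with radiotherapy treated in the same way.

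**The concern.** The two documents describe different designs. Both statements are current text, and nothing reconciles them.

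Centre is the only factor other than treatment that the SAP mentions for efficacy. If there is one centre, that mention does nothing, and what remains for scores is an unadjusted comparison of changes. Two things are at stake. A report written from the SAP could describe the trial as multicentre when its protocol is not. And a trial with 30 patients per arm would give up the precision available from a baseline score that its own change analysis already needs.

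**Working it through.** **1. The plan's own figure.** 2 arms x 30 = 60, which agrees with protocol sections 1, 2 and 5.1. No effect size, SD or power is stated, so nothing further can be reproduced.

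**2. What a centre term contributes.** For 60 patients, take a design matrix with intercept, arm and centre indicators. The centre degrees of freedom are the rank with the centre columns minus the rank without them.

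| Centres | Centre df |
|---|---|
| 1 | 0 |
| 2 | 1 |
| 3 | 2 |

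With one centre the column equals the intercept and the term drops out. The treatment estimate, its standard error and its p-value are those of the model without centre.

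**3. Precision of ANOVA of changes against ANCOVA.** Let rho be the correlation between baseline and follow-up score, with equal SDs at both times (assumption; the documents give neither).

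- Variance of a change: 2 x SD² x (1 - rho).
- Residual variance under ANCOVA: SD² x (1 - rho²).
- Ratio: (1 + rho)/2. The baseline score therefore explains a share R² = (1 - rho)/2 of the variance of change.

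Power below is two-sided at 0.05 (SAP section 2), 30 per arm, for an assumed effect of 0.5 SD of the change. It uses a normal approximation and ignores the one degree of freedom spent on the covariate.

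| rho (assumed) | R² | Power |
|---|---|---|
| no adjustment | 0 | 49.1% |
| 0.9 | 0.05 | 51.1% |
| 0.8 | 0.10 | 53.2% |
| 0.6 | 0.20 | 58.1% |
| 0.4 | 0.30 | 63.9% |

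**4. Exposure to chance imbalance in the baseline score.** With 30 per arm, the standard error of the baseline difference is SD x sqrt(2/30) = 0.258 SD. Given a baseline difference b, the ANOVA of changes is off by (1 - rho) x b, in favour of the arm that started worse. For a difference of one standard error:

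- rho = 0.4: 0.6 x 0.258 = 0.155 SD
- rho = 0.9: 0.1 x 0.258 = 0.026 SD

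These errors average to zero over randomisations. ANCOVA on the baseline score removes them.

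**5. Anticancer treatment, taken separately.** Allocation is not stratified for it. If 30%, 50% or 70% of patients are treated (assumed), two independent binomials of size 30 give a chance of 12.0%, 15.5% or 12.0% that the arms differ by at least 20 percentage points (6 of 30). What such a difference does to the estimate depends on the effect of anticancer treatment on the scores, which the documents do not give.

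**The case against.** The strongest reply is that the quoted error has no numerical consequence. The SAP only asks for the centre effect to be considered, none of the tests it names contains a centre term, and a one-level term drops out. That stands. A reader might infer that the efficacy analysis cannot be fitted as described. The documents do not support this, because the ANOVA of changes runs with or without the centre sentence.

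A reader might also count the multicentre statement as made twice, since a near-identical sentence follows it. Such doubled sentences occur throughout both documents and look like an artefact of the text, so this is one statement.

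A third tempting inference is that the centre error is the reason anticancer treatment goes unadjusted. It is not: a working centre term would not have adjusted for it either. The omission is separate, and putting a gain on it needs both the share of patients treated and the size of the effect. For patients already on treatment at entry, part of any effect may already be in the baseline score. The background section of the protocol links anorexia to tumour type and stage, so anticancer treatment is not the only candidate covariate.

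Finally, the study is exploratory and randomised, so the unadjusted comparison is unbiased in expectation. That is true, and it limits the point to precision and correct description. It does not remove it, because the contradiction remains and the baseline score is already needed for the change analysis.

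**Conclusion.** The contradiction holds: multicentre in SAP section 2, one department of one hospital in protocol section 3, and no second site in the text available. If the protocol is right, the centre instruction carries 0 degrees of freedom and the scores are compared by an ANOVA of changes with no covariate.

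The treatment estimate is not biased. The cost is a wrong description of the design, lower precision, and exposure to chance imbalance at 30 per arm. Under equal SDs and a baseline to follow-up correlation of 0.4 to 0.9 (assumed), ANCOVA reduces the variance by 30% to 5%. At an assumed effect of 0.5 SD of the change, that is 64% to 51% power against 49%. The 0 degrees of freedom rests on the protocol alone; the precision figures rest on the assumptions. The documents give no basis for sizing the benefit of adjusting for anticancer treatment. This is a modest correction, worth making because it costs little.

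**What to change.** Confirm the number of centres and reconcile SAP section 2 with protocol section 3.

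- **If single-centre:** delete the multicentre and centre-effect text from the SAP and describe the trial as single-centre.
- **If several centres:** name them in the protocol and include centre in the efficacy model.

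In the single-centre case, replace the ANOVA of changes with an ANCOVA of each main score (the symptom-based anorexia form and the simplified appetite scale) on treatment and the baseline value of that score. This costs a few lines of SAP text and one model degree of freedom. It needs no new data, since the comparison with baseline already requires those values.

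As a separate, optional precision step, add anticancer treatment under way or planned at randomisation (yes/no) as a covariate, recorded before allocation. Treatment started later should not be used, because the arm could influence it. This costs one more degree of freedom and one baseline item.
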